### *Time to first hypoglycaemia*

To keep the analysis of hypoglycaemia consistent with the overall AE analysis, a patient without an event will be considered censored at the date of last trial drug intake + 7 days or date of death, if earlier. For further details refer to [Section 7.8.1.6](#).

### *Time to first investigator reported heart failure (based on narrow SMQ cardiac failure)*

Censoring will be performed as described above for the primary endpoint.

### *Endpoints based on laboratory data only*

Patients who already fulfil the respective condition at baseline are not considered in the number of patients at risk for this endpoint.

If a baseline laboratory measurement is not available for the parameter of interest, it is assumed that the patient did not experience the condition corresponding to the endpoint at baseline and the patient is included in the patients at risk for this endpoint.

Patients without an event and available post-baseline laboratory measurements will be considered censored at the date of last laboratory sampling of the corresponding parameter. Patients with missing baseline laboratory required to derive a change from baseline and patients without laboratory data following the baseline measurement will be censored on the day of randomisation or date of first study drug intake, respectively..

### *Composite endpoints based on laboratory data and adverse events*

Only patients that are included in the analyses for all components of the composite endpoint will be included in the analysis of the composite.

Of those, a patient with at least one event in any of the components of the composite will be considered to have an event and the date of the first event will be used for the composite endpoint.

A patient without an event will be considered censored at the earliest of all censoring dates of the component endpoints.

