The End of Treatment Visit (EOT) activities will be performed when a patient discontinues study treatment permanently.

A follow-up visit will take place 30 days after the EOT visit. Patients who discontinue study drug prematurely should be observed until study end as if they were still receiving blinded study treatment, but no (safety) laboratory sampling (including pregnancy test), ECG or vital signs will be required. If a patient who prematurely discontinued study drug is not willing to return at the pre-defined regular visit schedule at minimum a yearly telephone call and a telephone call at study end will be required, to document the occurrence of outcome events and vital status. If possible, also other AE's and concomitant therapy changes since last visit might be recorded.

Patients should keep their antidiabetic medication stable for the course of the trial (except prior SU or glinide treatment which should be stopped at V2. SU/glinide should not be taken in the morning of Visit 2).

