#### *Endpoints of CV death, non-CV death and all-cause mortality*

A patient who did not die/died from another event will be censored at the latest date of the dates as described above, (for e.g. the primary endpoint) and the date of vital status (if alive)/ date last known to be alive (if LTFU)/ date of death (if died from another than event of interest).

Censoring rules and their application:

- 0-days censoring will be used for sensitivity analysis on TS (label: TS+0)
- 7-days censoring will be used for all adverse events - for hypoglycemia refer below (label: TS+7)
- 30-days censoring will be used for sensitivity analysis done on PPS (label: PPS) and OS (label: OS) and as additional sensitivity analysis regarding censoring on TS (label: TS+30)

All of the above mentioned x-day censoring rules will be handled as follows:

Patients who did not experience the event will be censored at the earliest date between the individual day of trial completion and x days after last intake of study drug. For this analysis events will be considered that occurred not later than x days after last intake of study drug, or until individual day of trial completion, whichever is earlier.

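### Composites of laboratory and adverse-event components (SAP 6.8.3): event-free patients are censored at the earliest component date, but events have no matching cut-off, which matters where component follow-up ends at different times

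*SAP*

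**What the plan says.** SAP 6.8.3, under its heading on composites of laboratory data and adverse events, has one rule for patients with an event and another for the rest.

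- Events: "a patient with at least one event in any of the components of the composite will be considered to have an event", dated at the first such event.
- No event: "A patient without an event will be considered censored at the earliest of all censoring dates of the component endpoints".

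Other text fixes the component dates.

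- Laboratory components (SAP 6.8.3): "Patients without an event and available post-baseline laboratory measurements will be considered censored at the date of last laboratory sampling of the corresponding parameter". In addition, "patients without laboratory data following the baseline measurement will be censored on the day of randomisation or date of first study drug intake", so these patients stay in the analysis with about one day at risk.
- After early drug discontinuation, Protocol 3.3.4.1 keeps patients under observation to study end, "but no (safety) laboratory sampling (including pregnancy test), ECG or vital signs will be required".
- Adverse events (SAP 6.8.3): "7-days censoring will be used for all adverse events". SAP 7.8.1.3.2 lets some approaches use 30 days or the date of trial termination instead.
- Cardiovascular outcome components (SAP 6.8.3) run to the last documented study visit, regardless of drug intake.

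For its x-day analyses SAP 6.8.3 limits both sides alike: "events will be considered that occurred not later than x days after last intake of study drug", and event-free patients are censored at that same limit. The composite rule has no such limit on events.

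**The concern.** Whether a stretch of follow-up enters the analysis should not depend on what happens later. Take two patients who stop drug and sampling at year 2. One has a clinical component event at year 5 and contributes five years and one event. The other stays event-free to year 6 and contributes two years. Between years 2 and 5 only the patient who goes on to have an event is in the risk set.

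Dropping event-free time while keeping the events raises the rate. The excess grows with the gap between the last sample and the end of clinical follow-up, so unequal discontinuation between arms could move the treatment comparison with no true difference.

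**Working it through.** The documents give no figure for these composites, so there is none to reproduce. The check takes a case that can be done by hand, then a simulation with trial-like follow-up.

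**Hand case.** 100 patients, laboratory data to year 2, clinical follow-up to year 7, clinical hazard λ = 0.018 per year, no laboratory events.

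- Events as written: 100 × (1 − e^(−0.018×7)) = 11.8.
- Time from patients with an event: 100 × [(1 − e^(−0.126))/0.018 − 7e^(−0.126)] = 40.6 years.
- Time from event-free patients, cut at year 2: 100 × e^(−0.126) × 2 = 176.3 years.
- Rate as written: 1000 × 11.8/216.9 = 54.6 per 1000 patient-years, about three times the true 18.
- With events also cut at year 2: 100 × (1 − e^(−0.036)) = 3.54 events over 3.54/0.018 = 196 years, which returns 18.

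This is an extreme case. It shows the mechanism, not the likely size.

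**Simulation inputs.**

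- Follow-up uniform from 5.4 to 7.4 years (Protocol 7.6: 2 years' accrual, 5.4 years' follow-up).
- Clinical hazard 0.018 per year, borrowed from the primary endpoint rate in Protocol 7.6.
- Assumed: laboratory hazard 0.03 per year, seen at the next 16-weekly sample; discontinuation 3%, 6% or 10% per year; last sample at drug stop.
- Rate = 1000 × patients with event / years at risk, with 400,000 patients per scenario. As written, events count to the end of their own component and event-free patients stop at the earliest component date. With a common cut-off, both stop there.

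**Clinical components followed to study end:**

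| Discontinuation per year | As written | Common cut-off | Excess | Events after the earliest component date |
|---|---|---|---|---|
| 3% | 48.7 | 47.1 | +3% | 4% |
| 6% | 50.2 | 47.0 | +7% | 7% |
| 10% | 52.5 | 46.8 | +12% | 12% |

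With the laboratory hazard lowered to 0.01, or the clinical hazard to 0.01, the full range of excess is +2% to +21%.

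**Shorter clinical window.** At last dose plus 7 days the excess is below 0.1% at all three discontinuation rates. At 16 weeks it is about 1% or less.

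**No post-baseline sample.** If 2% of patients have none, at 6% discontinuation and follow-up to study end, the rates are 50.6 against 46.9 (+8%).

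**Between arms, equal true hazards, follow-up to study end.** Rate ratio of the arm with less discontinuation to the arm with more:

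- 5% against 7% per year: 0.98 as written, 1.00 with a common cut-off.
- 4% against 8% per year: 0.96 as written, 1.01 with a common cut-off (simulation error about 1%).

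**The case against.** **The composites are not visible.** Their components, windows and any endpoint-specific cut-off may be in text that is not public. This stands, and it makes any statement of size conditional. SAP 6.8.1 does provide for composites that mix components timed from randomisation with components timed from first drug intake. That fits outcome components followed past drug stop, but does not establish them.

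**Section 6.8 may already supply the cut-off.** Its opening says that the time intervals determine the start and end for deriving occurrence. That could be read as limiting countable events to the time at risk. It names no cut-off for composites, however, and a year-5 clinical event lies inside its own component's interval. The text is at best ambiguous.

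**Sampling not required is not sampling never done.** Drug may be restarted under Protocol 3.3.4.1, and the Flow Chart schedules laboratory tests at the 30-day follow-up visit. If half of those who discontinue keep being sampled, the 7% excess falls to about 3%, and the rate ratio for 10% against 6% discontinuation falls from about 1.05 to 1.02. This tempers the size. It does not work in one direction only: with a 7-day clinical window and half still sampled, laboratory events fall after the clinical cut-off and the excess is about 5%.

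**Censoring at the earliest date is right.** It agrees with the SAP's principle for cardiovascular endpoints of censoring at the last date known event-free. Agreed: the fault lies only in the missing limit on events.

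A reader might infer that all late follow-up is lost unless an event occurs. That holds only for patients in whom one component's observation has ended; patients still under observation for every component contribute event-free time as usual.

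**Conclusion.** The mismatch between the event rule and the censoring rule is in the SAP text, and no other passage clearly removes it. Its effect depends on the component windows. With clinical follow-up to study end, the rate is overstated by about 3% to 12% at 3% to 10% discontinuation per year, given the assumed laboratory hazard of 3% and clinical hazard of 1.8% per year. With a 7-day clinical window and sampling that ends at drug stop, it is negligible.

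The documents do not support three stronger readings.

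- That rates of these composites are overstated in every case: the windows are not shown.
- That one of the two treatments is disadvantaged: the documents give no discontinuation rate by arm, and the shift of a few percent needs an assumed imbalance.
- That confirmatory results are at risk: the primary and first key secondary endpoints contain no laboratory component. The second and third key secondary endpoints use HbA1c, and the second also hypoglycaemia, but they are responder proportions tested by chi-square with no censoring.

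Severity is minor: non-confirmatory endpoints and a rule that one sentence can correct.

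**What to change.** In SAP 6.8.3, apply one cut-off to all patients in these composites: take each patient's earliest component censoring date, count a composite event only if it occurs on or before that date, and otherwise censor there. As a sensitivity analysis, count all clinical events and censor event-free patients at the end of clinical follow-up.

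The cost is in events rather than data collection. Clinical events after the last sample leave the main version, about 4% to 12% of composite events under the assumptions above with follow-up to study end. Patients with no post-baseline sample lose all their clinical events from it. Both groups of events appear only in the sensitivity analysis, so the report should give their numbers by arm. If the component windows already coincide, the sentence changes almost nothing.

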## **6.8.4 Definition of lost-to follow-up**

If a patient could not be followed-up (vital status could not be collected) at the end of study (considering a certain close-out period), that patient will be flagged as Lost To Follow Up (LTFU). Patients who died are not considered LTFU.

## **7. PLANNED ANALYSIS**

A general overview on patient disposition will be provided by treatment group and in total and presented in the clinical trial report by frequency tabulations. This will include the number of patients enrolled, entered/randomised, treated as well as those who did/ did not prematurely discontinue trial medication, did/did not prematurely discontinue from trial.

The frequency of patients with important protocol violations and the frequency of patients in different analysis sets will be presented by treatment group.

For End-of-text tables and appendix tables, the set of summary statistics is: N / Mean / SD / Min / Median / Max. Q1 (lower quartile) and Q3 (upper quartile) will be shown, if appropriate.

The 1st and 99th percentiles might be substituted for minimum and maximum in tables with open-ended values to safeguard against implausible extremes.

Geometric means and ranges will be added to the presentation or replace the presentation of mean and standard deviation for parameters which rather follow a log-normal distribution than a normal distribution.

Tabulations of frequencies for categorical data will include all possible categories and will display the number of observations in a category as well as the percentage (%) relative to the respective treatment group. Percentages will be rounded to one decimal place. The category missing will be displayed only if there are missing values.

Statistical parameters will be displayed to a defined number of decimal places as specified in the BI guideline “Reporting of Clinical Trials and Project Summaries” [\(3\)](#).

### **7.1 DEMOGRAPHIC AND OTHER BASELINE CHARACTERISTICS**

Descriptive analysis of the following demographic characteristics and variables measured at baseline will be presented by treatment groups and in total for the TS:

- Gender, race, ethnicity, country, age (continuous and categories of <55 years to >=85 in steps of 5 years),
- Height, weight (continuous and categorical), BMI (continuous and categorical), waist circumference
- Smoking history and Alcohol status
- Duration of formal education in years
- eGFR (continuous and categorical)
- Baseline HbA1c (continuous and categorical) and FPG (continuous and categorical)
- Time since diabetes mellitus type 2 was first diagnosed (continuous and categories of <=1 year, >1 to <=5 years, >5 to >= 10 years, >10 years)

## **7.2 CONCOMITANT DISEASES AND MEDICATION**

### Relevant medical history/concomitant diseases

Relevant medical history/concomitant diseases will be coded using the most recent version of the Medical Dictionary for Regulatory Activities (MedDRA).

Frequency tabulations of the following concomitant diseases as obtained at baseline will be presented by treatment group and in total based on the TS:

- Cardiovascular risk factor categories: Previous vascular disease, Evidence of vascular related end-organ damage, Multiple CV risk factors (hypertension, current smoking, dyslipidaemia, Type 2 Diabetes Mellitus >10 years) as well as combinations ([Section 6.4](#))
- Relevant medical history (presence of baseline conditions within the previous 6 month: Diabetic retinopathy, Diabetic nephropathy, Diabetic neuropathy, Diabetic foot, Coronary artery disease, Peripheral artery occlusive disease, Cerebrovascular disease and Hypertension

The number of patients (including percentages) with at least one concomitant disease (except diabetes mellitus type 2) at baseline will be presented.

Concomitant diagnoses by MedDRA System Organ Class (SOC) or Preferred Terms at screening with incidence of  $\geq 1\%$  in at least one treatment group will be summarised by treatment group and in total in a frequency table based on the TS.

### Concomitant medication

All frequency tabulations will be performed on the TS.

In general, any therapy with the start date equal to the date of first trial drug intake is considered as being taken after first trial drug intake.

Overall concomitant medication use (excluding antidiabetic/background therapy) with an incidence of  $\geq 1\%$  in at least one treatment group per WHO-DD preferred name will be summarised by Anatomical-Therapeutic-Chemical classification level 3 (ATC3). Summaries will be presented for concomitant therapies taken during screening and those taken after first drug intake.

Separate summaries of use of acetylsalicylic acid (ASA), antihypertensives, lipid lowering drugs, P-gp or CYP 3A4 inhibitors and anti-coagulants during screening and those taken after first drug intake will be presented.

Antidiabetic therapies including background therapies taken at screening as well as those started after the date of first trial drug intake will be presented, with categorisation into monotherapy/combination therapy and the number of (oral) antidiabetic drugs. Antidiabetic therapies at screening will be linked to the visit 1a HbA1c to reflect the different categories of inclusion criterion 2.

An antidiabetic therapy that is not a background therapy is considered as being taken at screening, if the start date was before the date of IC and the end date was not earlier than 10 weeks prior to IC. As the start and stop date of the protocol-defined background medication of alpha-glucosidase inhibitor and/or metformin is not recorded in the eCRF, it is assumed, that this background medication was already taken at screening.

Summaries on the total daily dose of metformin at the date before first trial drug intake and last date of trial drug intake will be provided, this includes a categorisation into  $\leq 1500\text{mg}$  or  $>1500\text{mg}$ .

The number of patients with a change in background therapy at any time starting from the date of first intake of trial drug will be presented for metformin as well as alpha-glucosidase inhibitor.

### **7.3 TREATMENT COMPLIANCE**

Compliance will be analysed descriptively

A table showing the frequency of patients within (yes) and respectively outside (no) of 80%-120% compliance will be given, presenting information for all visits for each treatment group, as well as for the total of all patients, based on the treated set.

The percent compliance was to be calculated by the investigator as described in Section 4.3 of the CTP.

The time windows as described in [Section 6.7.3](#) will also be used for compliance, except that the time window end for the last visit is determined by the last information entered for a patient. This means, that whenever compliance is documented due to premature treatment discontinuation, the information will be assigned to the respective week. That may result in varying denominators of patients with compliance information over time, as a patient might stop study drug permanently and restart again.

Whenever compliance information has been documented more than once within the same time window, the following rules apply:

- Compliance outside of 80-120% at least once in that window: This information is used and no is displayed
- Compliance always inside 80-120% in that window: This information is used and yes is displayed
- Compliance always missing in that window: Missing is displayed
- Compliance missing at least once in that window and the other values is inside the window: The compliance is considered as being inside 80-120%.

### **7.4 PRIMARY ENDPOINT**

#### **7.4.1 Primary analysis**

For the primary endpoint of time to the first occurrence of any of the following CEC confirmed adjudicated components of the primary composite endpoint: CV death (including

fatal stroke and fatal MI), non-fatal MI (excluding silent MI), or non-fatal stroke an ITT-analysis (as randomised) on the TS will be performed. The analysis will be performed on TS with patients considered as randomised (intention-to-treat) and all events up to individual day of trial completion considered.

The randomised study treatment will be used to assign patients and events to treatment groups; all adjudicated events which occur until study end will be taken into account (i.e. independent of whether or not a patient was still on study medication).

The time to the primary endpoint will be derived from the date of randomisation.

The one-sided overall significance level will be  $\alpha=2.5\%$ . As described in the CTP, the DMC will perform formal interim analyses. The significance levels for the analyses are denoted by  $\alpha_i$ ,  $i=1, \dots, K$ , where K is the total number of analyses.

The O'Brien & Fleming alpha-spending function defined the significance level for the first interim analysis on 4P-MACE.

Due to the change of the primary endpoint after the first DMC interim analysis a Bonferroni adjustment will be applied in addition, to control the overall alpha level.

That means, the alpha spent at the first DMC interim analysis (performed for 4P-MACE and based on the O'Brien & Fleming alpha-spending function) is subtracted from the initial overall alpha. The O'Brien & Fleming alpha spending function based on the new overall alpha (after additional Bonferroni adjustment) defines the allocation of the still available overall significance level for the second interim analysis and the final analysis.

#### 7.4.1.1 Statistical Methods

For the primary analysis a regression analysis using Cox's proportional hazards model including a term for treatment will be applied to compare linagliptin with glimepiride. Breslow's method will be used for dealing with ties.

The hazard function of an event for patient j at time t is assumed to have the form

$$h_j(t) = \exp(\beta_1 x_{1j}) h_0(t), j=1, \dots, n,$$

where

- $h_0(t)$  is the non-negative baseline hazard function for a patient with a value of zero for the explanatory value  $x_{1j}$
- $\beta_1$  is the (unknown) coefficient of the explanatory variable  $x_1$
- $x_{1j}$  is an indicator variable representing the treatment group for patient  $j=1, \dots, n$ .

The hazard ratio (HR) for the effect of treatment (linagliptin vs. glimepiride) will be presented with the corresponding  $(1-2*\alpha_i)*100\%$  confidence interval (CI), the corresponding one-sided p-value for the non-inferiority test (NI margin 1.3), the one-sided p-value for the superiority test, and the two-sided p-value for the null hypothesis of equality based on the Wald chi-squared statistic.

The proportional hazards assumption will be explored by plotting  $\log(-\log(\text{survival function}))$  against the log of time by treatment group and checked for parallelism. The interaction of treatment with log of time will be included in the model described above for an exploratory analysis. Further, Schoenfeld residuals will be plotted against time and  $\log(\text{time})$ .

The probability of the primary endpoint event over time will be displayed by treatment using Kaplan Meier (KM) estimates, which includes the presentation of certain quantiles of the failure times (e.g. 2.5%, 5%, 7.5% and 10% quantiles) and Kaplan-Meier rates after specific number of years.

Any pointwise  $(1-2*\alpha_i)*100\%$  CIs for KM failure rates will be determined using Greenwood's variance estimate.

The two-sided p-value resulting from the log-rank test will be presented.

Tabular and graphical displays will present the (cumulative) number of patients at risk, failures as well as censored patients over time.

Descriptive statistics will display the number of patients at risk, the number of patients with event, the incidence (proportion of patients with event), the time at risk for event and the incidence rate (number of patients with event per 1000 years at risk) per treatment group.

